Visit Interval Tolerance (days)		±3	_	±3		±3	±3	±3	±3	±3	±3	±3	±3	±3	±3	±3	±3	±3	b Visit 6 must not occur on the same day as Visit 5.
Visit Detail			F	Т			Т	F	Т	Т	Т	F	Т	Т	Т	F	Т	F	T = telehealth visit F = fasting visit
Review SMBG 6-point profiles			X															X	Review profiles collected in preceding week. See Section 8.1.1.1.
Paper Patient-Reported Ou	itcome	es																	
Treatment-Related Impact Measure - Diabetes (TRIM-D)			X															X c	c At Visit 18 or after, if a participant changes from the autoinjector to the prefilled pen, conduct this procedure on the day the change occurs.
Diabetes Injection Device Experience Questionnaire (DID-EQ)																		Х°	changes from the autoinjector to the prefilled pen, conduct this procedure on the day the change occurs.
Electronic Patient-Reporte	d Outo	comes																	
Diabetes Treatment Satisfaction Questionnaire - Status (DTSQ-s)			X																
Diabetes Treatment Satisfaction Questionnaire - Change (DTSQ-c)																		Х°	c At Visit 18 or after, if a participant changes from the autoinjector to the prefilled pen, conduct this procedure on the day the change occurs.
Simplicity of Diabetes Treatment Questionnaire (SIM-Q)																		Х°	c At Visit 18 or after, if a participant changes from the autoinjector to the prefilled pen, conduct this procedure on the day the change occurs.

Study I8H-MC-BDCW Table 1	& L	een ead- n								Trea	itmen	t							Comments
Visit Number	1	2	3	4	5	6	7	8	9	10	11	12	13	14	15	16	17	18	
Weeks from Randomization	-3	-2	0	1	1 a	2 b	3	4	5	6	7	8	9	10	11	12	14	16	a Visit 5 occurs 3 days after Visit 4 ± 1 day.
Visit Interval Tolerance (days)		±3	_	±3		±3	±3	±3	±3	±3	±3	±3	±3	±3	±3	±3	±3	±3	b Visit 6 must not occur on the same day as Visit 5.
Visit Detail			F	Т			Т	F	Т	Т	Т	F	Т	Т	Т	F	Т	F	T = telehealth visit F = fasting visit
Basal Insulin Experience Likelihood of incorporating into routine																		Х°	changes from the autoinjector to the prefilled pen, conduct this procedure on the day the change occurs.
Laboratory Tests and Samp	ole Co	llectio	ns																
Hematology	X		X													X			
Hemoglobin A1c (HbA1c)	X		X			X		X				X				X		X	
Clinical chemistry	X		X													X			
Glucose								X				X						X	
Lipid panel			X													X			
Urinalysis	X																		
Serum pregnancy	X		X																Collect for WOCBP only.

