## 6.3. Measures to Minimize Bias: Randomization and Blinding

#### Randomization and stratification

All participants will be centrally assigned to randomized study intervention using an IWRS. Before the study is initiated, the login information and directions for the IWRS will be provided to each site.

Participants will be randomly assigned in an 1:1 ratio to LY3209590:insulin glargine.

Participants will be stratified based on

- country
- HbA1c stratum at Visit 1 (<8% and  $\ge8\%$ ), and
- GLP-1 RA use at randomization, regardless of oral or injectable administration, (Yes/No).

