# 1.2. Study Design

- This is a Phase 3, parallel-design, open-label, randomized control, treat-to-target study to evaluate the efficacy and safety of LY3209590 administered once-weekly compared to insulin glargine administered daily in adult participants with T2D that are insulin naïve.
- The study includes a 3-week screening and lead-in period, a 52-week treatment period, and a 5-week safety follow-up period after the last visit in the treatment period.
- Participants will be randomly assigned to receive daily insulin glargine or weekly insulin LY3209590. Stratification will be by country, HbA1c stratum at Visit 1 (Week -3) (<8.0%, ≥8.0%), and GLP-1 RA use at randomization, regardless of oral or injectable administration.
  - o Participants randomly assigned to insulin glargine
    Participants randomly assigned to insulin glargine will start on 10 U/day and will
    have weekly dose adjustments based on FBG and hypoglycemia events.
  - Participants randomly assigned to receive LY3209590
     Participants randomly assigned to receive LY3209590 will be on a fixed dose escalation for at least the first 16 weeks of the study. Participants will start LY3209590 on a fixed dose of 100 U per week and will escalate the LY3209590 dose every 4 weeks as required to the set doses of 150, 250, and 400 U per week.

Treat-to-target dose adjustments will be based on FBG of 80 to 130 mg/dL (4.4 to 7.2 mmol/L) and hypoglycemia events.

Dose administration will be via a fixed dose autoinjector.

After Week 16, if a participant who has received the fixed dose of 400 U per week for at least 4 weeks has a median FBG level >130 mg/dL, then the investigator should transition the participant to titratable doses using a prefilled pen. This will provide more dosing flexibility and allow dose titrations above 400 U per week.

If a participant transitions from the fixed dose autoinjector to a prefilled pen, they must continue using the prefilled pen for the remainder of the study.

• Rescue therapy will be considered during the treatment period if the participants meet the protocol criteria of severe, persistent hyperglycemia.

If a participant is transitioning to a prefilled pen, investigators should:

- o ensure that the transition does not occur at the same time as initiation of rescue therapy, and
- o wait for at least 4 weeks after the first dose with the LY3209590 prefilled pen.

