Analysis	Baseline Observations	Postbaseline Observations
HbA1c (treatment regimen	The baseline is the last non-missing	Planned measurements at Visit 33
estimand)	assessment prior to or at the first	(primary endpoint, Week 52) and
	day of study treatment.	Visit 25 (secondary endpoint, Week
		26) in EAS1. Use unplanned
		measurements (collected on the same
		visit day) if no planned
		measurement.
		Multiple imputation approach will be
		used to impute missing observations
		at Visit 33 (Week 52) and Visit 25
		(Week 26).
HbA1c (efficacy estimand)	The baseline is the last non-missing	• Visits 6, 8, 12, 16, 18, 25, 28,
	assessment prior to or at the first	and 33 (Weeks 2, 4, 8, 12, 16,
	day of study treatment.	26, 36, and 52) in EAS2 for
		MMRM
		For sensitivity analysis to
		compare the treatment effect of
		LY3209590 with autoinjector
		and insulin glargine:
		o LY3209590: Visits prior to
		or at the time of switch to
		prefilled pen in EAS2 for
		MMRM
		o Glargine: Visits 6, 8, 12, 16,
		18, 25, 28, and 33 (Weeks 2,
		4, 8, 12, 16, 26, 36, and 52)
		in EAS2 for MMRM
		Planned measurements at scheduled
		visits will be included. Use
		unplanned measurements (collected
		on the same visit day) if no planned
		measurements.

Analysis	Baseline Observations	Postbaseline Observations
Analysis Fasting glucose by SMBG	Baseline Observations  The baseline period is the lead-in period up to the day of first dose of study treatment. Baseline will be derived as the average of all fasting glucose measurements between V2 date and the first dose date.	All available data after the day of first dose of study treatment up to Visit 33 (Week 52) in EAS2 for MMRM (efficacy estimand).  Values at each visit will be derived as average of all fasting glucose measurements from the day post prior visit up to the day of next visit.  Data at Visit 33 (Week 52), Visit 25 (Week 26), and Visit 18 (Week 16) in EAS1 for ANCOVA with multiple imputation for missing data (treatment regimen estimand).  For sensitivity analysis to compare the treatment effect of LY3209590 with autoinjector and insulin glargine:  LY3209590: after the day of first dose of study treatment up to the visit prior to or at the time of switch to prefilled pen in EAS2 for MMRM (efficacy estimand).  Glargine: after the day of first dose of study treatment up to Week 52 (Visit 33) in EAS2 for

Analysis	Baseline Observations	Postbaseline Observations

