#### 4.4.2. Supportive Secondary Endpoints

#### 4.4.2.1. Other Efficacy Endpoints

The analyses for the other supportive efficacy endpoints of insulin dose, and patient-reported outcomes will be based on the EAS2 data. The analysis of change from baseline for HbA1c at Week 26 and fasting glucose by SMBG at Week 16, 26 and 52 will be performed for both treatment regimen estimand and efficacy estimand.

For treatment regimen estimand, only participants with an observation at baseline or at the endpoint visit will be included in the analysis. The missing baseline will be imputed using multiple imputation under assumption of missing at random. Missing data at the endpoint visit will be imputed using either retrieved dropout or return-to-baseline multiple imputation approach determined by the criterion described for the primary efficacy endpoint in Section 4.3.2. ANCOVA analysis will be conducted similar to that for the primary endpoint. An additional term of baseline HbA1c stratum (<8.0%,  $\ge8.0\%$ ) will be added into the model for the endpoints other than HbA1c.

For efficacy estimand, participants with baseline and at least one post baseline observation will be included in the analysis. The longitudinal observations of actual and change from baseline in HbA1c to Week 26 will be analyzed using the same MMRM model as for the efficacy estimand described in Section 4.3.2. The analyses of other continuous efficacy measures (fasting glucose measured by SMBG) will use an MMRM model similar to that for the primary endpoint with an additional term of baseline HbA1c stratum (<8.0%, ≥8.0%). If a subject does not indicate which BG measurement was fasting, the FBG value will be assigned programmatically by designating the FBG as the first measurement between 5am-10am. These programmatically derived FBG values will also be included in the analysis. The variance-covariance structure in the MMRM models for fasting glucose from SMBG and insulin dose will be based on compound symmetry.

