The analysis of study insulin dose will use an MMRM model on the EAS2 data with treatment, strata (country, GLP-1 RA treatment at randomization, and baseline HbA1c stratum [<8.0%, ≥8.0%]), visit, and treatment-by-visit interaction as fixed effects. The average weekly dose during each visit for individual participants will be used in the analysis. In the LY3209590 group, the average dose of each visit (that is, average of weekly doses since last visit) will be used as the average weekly dose. In the insulin glargine group, the average weekly dose will be calculated by the average daily dose multiplying by 7. The analysis will be repeated for average daily dose in U and daily dose in U/kg. The body weight at the visit will be used to calculate the daily dose in U/kg at the same visit.

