## 6. Supporting Documentation

## 6.1. Appendix 1: Demographic and Baseline Characteristics

Demographic and baseline characteristics including but not limited to age (years), age groups ( $<65, \ge 65$  and  $<75, \ge 75$  and  $<85, \ge 85$  years), sex, ethnicity, race, country, region, height, weight (kg), BMI (kg/m2), BMI groups ( $<25, \ge 25$  and  $<30, \ge 30$  and  $<35, \ge 35$  kg/m²), eGFR groups ( $<30, \ge 30$  and  $<60, \ge 60$  and  $<90, \ge 90$  mL/min/1.73 m²), duration of diabetes (years), HbA1c at screening, HbA1c stratum at screening (<8.0% and  $\ge 8.0\%$ ), baseline HbA1c, baseline HbA1c stratum (<8.0% and  $\ge 8.0\%$ ), fasting serum glucose (mmol/L and mg/dL), GLP-1 RA treatment at randomization, and number of non-insulin antihyperglycemic medications in use at randomization will be summarized by treatment group using the mITT and Randomized Population (if different from the mITT).

Continuous measures will be summarized using descriptive statistics and treatment difference will be analyzed using the analysis of variance. Categorical measures will be summarized using sample size, frequency, and percentage and treatment difference will be analyzed using Chi-squared test.

The by participant listing of demographic and baseline characteristics will be provided for Randomized Population.

Historical conditions are conditions that end prior to inform consent and preexisting conditions are conditions that are still ongoing at inform consent. The number and percentage of participants with historical conditions will be summarized by treatment group using MedDRA PT using the mITT and Randomized Population (if different from the mITT). Events will be ordered by decreasing frequency within SOC. Similar summary will also be provided for preexisting conditions.

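### Several supportive models adjust for a baseline HbA1c stratum in place of the Visit 1 stratum used at randomisation and without continuous HbA1c; the analyses stay valid but lose a little precision

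*SAP*

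**What the plan says.** **Randomisation.** Protocol 6.3 stratifies by country, GLP-1 RA use and "HbA1c stratum at Visit 1", cut at 8%. SAP 1.2 agrees: "Stratification will be by country, HbA1c stratum at Visit 1 (Week -3").

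**Baseline.** The schedule of activities (Protocol 1.3.1, row "Hemoglobin A1c (HbA1c")) has HbA1c taken at Visit 1 and again at Visit 3. For HbA1c, SAP 4.1 states: "The baseline is the last non-missing" assessment up to the first day of treatment. That is normally Visit 3.

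**Two strata listed.** SAP Appendix 1 will summarise "HbA1c at screening, HbA1c stratum at screening", and then, separately, baseline HbA1c and a baseline HbA1c stratum with the same 8.0% cut.

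**Models that use the baseline stratum.**
- SMBG fasting glucose, both the ANCOVA and the MMRM (SAP 4.4.2.1): "An additional term of baseline HbA1c stratum".
- Insulin dose (SAP 4.4.2.1): "strata (country, GLP-1 RA treatment at randomization, and baseline HbA1c stratum".
- TRIM-D (SAP 4.4.2.3.1) and the DID-EQ Device Characteristics subscale (SAP 4.4.2.3.5).
- SMBG variables (SAP 4.5.3), and fasting serum glucose through the reference in SAP 4.5.1 back to 4.4.2.1.

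**Models that use baseline HbA1c itself.** These are the primary and key secondary HbA1c models (SAP 4.3.2, 4.4.1.2), the binary HbA1c endpoints (4.5.1) and the hypoglycemia models (4.6.3.1).

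**The concern.** A participant near 8% can be in one group at Visit 1 and in the other at Visit 3. If the model term is cut from the Visit 3 value, the factor that governed allocation is not in the model, although three of these sections list the term under strata, beside GLP-1 RA use at randomisation. Leaving a prognostic stratification factor out entirely tends to make standard errors too large. Cutting a measured covariate at one threshold also discards information that the SAP keeps in its other models. Two programmers could reasonably build different variables from the present text. At stake is the precision and reproducibility of a group of supportive endpoints.

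**Working it through.** **The plan's own figures.** The plan quantifies nothing on this point. Its sample-size claims do reproduce: 284 completers per arm with SD 1.1% give power 99.1% for the 0.4% margin, and 90.1% for the 0.3% margin and for superiority at -0.3%. None of this depends on the term in question.

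**Which variable is meant.** SAP 4.1 ties baseline HbA1c to the last value up to first treatment. Appendix 1 lists "HbA1c stratum at screening" and the baseline stratum as separate items. Together these favour a re-cut of the pre-dose value. The model sections do not define the term.

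**Assumptions, because the documents give no figures.** Visit 1 HbA1c is normal with mean 8.2 and SD 0.9, truncated to the 7-10% entry range (resulting mean 8.31, SD 0.71). The Visit 1-to-Visit 3 difference has SD 0.2 to 0.5 points. The outcome depends on baseline HbA1c.

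**Change of stratum.** The share of participants in different strata at the two visits is 7.5%, 11.2%, 14.5% and 17.6% for difference SDs of 0.2, 0.3, 0.4 and 0.5.

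**Information kept by the cut.** The squared correlation k of the baseline stratum with continuous baseline HbA1c is about 0.61. A second set of assumptions (mean 8.0-8.4, SD 0.8-0.9) gives 0.615.

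**Loss of precision.** Let ρ be the share of outcome variance, after the other covariates, that continuous HbA1c explains. The confidence interval ratio, stratum against continuous, is sqrt[(1 − kρ)/(1 − ρ)].

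| ρ | k | Calculation | CI wider by |
|---|---|---|---|
| 0.01 (r = 0.1) | 0.615 | sqrt(0.99385/0.99) | 0.2% |
| 0.04 (r = 0.2) | 0.615 | sqrt(0.9754/0.96) | 0.8% |
| 0.09 (r = 0.3) | 0.615 | sqrt(0.94465/0.91) | 1.9% |
| 0.10 | 0.61 | sqrt(0.939/0.90) | 2.1% |
| 0.20 | 0.61 | sqrt(0.878/0.80) | 4.8% |
| 0.30 | 0.61 | sqrt(0.817/0.70) | 8.0% |

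**Visit 1 stratum alone.** Its squared correlation with baseline HbA1c falls from 0.566 to 0.406 as the difference SD goes from 0.2 to 0.5. The variance ratio against the re-cut stratum is (1 − 0.566 × 0.1)/(1 − 0.61 × 0.1) = 1.005 at the low end. At the high end it is (1 − 0.406 × 0.3)/(1 − 0.608 × 0.3) = 1.074. A straight swap would therefore raise variance by about 0.5% to 7%.

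**Validity.** The simulation ran 4,000 trials per scenario with 568 participants each. Allocation used blocks of 4 within the Visit 1 stratum (block size assumed).

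| Model term | Type I error, SD 0.3, ρ 0.2 | Type I error, SD 0.5, ρ 0.3 |
|---|---|---|
| No HbA1c term | 0.035 | 0.038 |
| Visit 1 stratum | 0.049 | 0.050 |
| Re-cut baseline stratum | 0.046 | 0.051 |
| Continuous baseline HbA1c | 0.045 | 0.054 |

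The simulation error at 5% is sqrt(0.05 × 0.95/4000) = 0.0034. Mean bias was at most 0.0024 outcome SD in any model.

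**The case against.** The strongest reply is that this is a choice between two valid prespecified covariate sets, for endpoints outside the controlled testing sequence. The re-cut stratum is measured before treatment, so adjusting for it is legitimate. It also predicts the outcome better than the Visit 1 stratum under the assumptions above. The size of the loss is assumed, and fasting glucose and TRIM-D already adjust for their own baseline, which points to the low end. The authors may simply have meant the randomisation stratum, since they list the term beside other randomisation factors. All of this stands. It limits the size of the point but does not remove it: the text is ambiguous, and the better covariate is already collected.

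A reader might infer more than the documents support:
- **That inference is invalid.** It is not. Only the model with no HbA1c term at all was clearly conservative.
- **That every continuous secondary endpoint other than HbA1c is affected.** Body weight uses the SAP 4.6 model, which has no HbA1c term. DTSQ, SIM-Q and the DID-EQ global items are compared by unadjusted Wilcoxon tests.
- **That the HbA1c subgroups in SAP 4.7.2 are compromised.** Grouping by HbA1c at the start of treatment is a legitimate choice, and the other subgroups there, such as age and eGFR, are not randomisation strata either.

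**Conclusion.** The point holds as one of specification and efficiency. The models listed above name a stratum that, on the SAP's own definitions, is most likely not the one used at randomisation, and they omit the continuous value. There is no bias and no type I error problem in the simulated scenarios. The primary and key secondary analyses and the sample size are untouched.

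The likely cost is confidence intervals wider by under 2% where HbA1c adds little beyond the other covariates, and by about 2% to 8% if it explains 10% to 30% of outcome variance. Insulin dose and the DID-EQ subscale are the likelier places for the larger loss, because neither model has a baseline of its own outcome. These sizes rest on assumed HbA1c variability and assumed HbA1c-outcome association. That the Visit 1 stratum alone does worse rests on the outcome following the pre-dose value. The change is worth making because it is almost free.

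**What to change.** In SAP 4.4.2.1, 4.4.2.3.1, 4.4.2.3.5 and 4.5.3, and so in 4.5.1 for fasting serum glucose, replace the baseline HbA1c stratum with the Visit 1 HbA1c stratum as recorded in the IWRS, and add continuous baseline HbA1c as a covariate. Make both changes together, because the Visit 1 stratum alone would slightly raise the variance. Leave the subgroup definitions in 4.7.2 as they are. The cost is SAP wording, settled before unblinding. Both variables are already collected, and Appendix 1 already plans to summarise HbA1c and its stratum at both time points.

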# **Height and Weight**

Height and weight will be measured as outlined in the SoA.

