# 1.1. Objectives, Endpoints, and Estimands

Objectives	Endpoints
Primary	
Demonstrate noninferiority of LY3209590 compared to insulin glargine for the treatment of T2D in adults	Change in HbA1c from baseline to Week 52
Key Secondary (Gated)	
Demonstrate superiority of LY3209590 compared to insulin glargine	Change in HbA1c from baseline to Week 52
Other Secondary	
Compare the effect of LY3209590 to insulin glargine in parameters of glycemic control	
 
Change from baseline to Week 26 for HbA1c
 
Change from baseline to Weeks 16, 26, and 52 for fasting glucose measured by SMBG
 
Insulin dose at Weeks 16, 26, and 52
 

Compare the effect of LY3209590 to insulin glargine on safety endpoints	
 
Incidence and rate of composite of Level 2 and 3 hypoglycemia events during the treatment period
 
Incidence and rate of composite of Level 2 and 3 nocturnal hypoglycemia events during the treatment period
 
Change from baseline to Weeks 26 and 52 in body weight
 

Compare the effect of LY3209590 to insulin glargine on patient-reported outcomes questionnaires	
 
Change from baseline to Weeks 26 and 52 for:
 
TRIM-D, and
 
DTSQ
 
Treatment experience at Weeks 26 and 52 for:
 
DID-EQ, and
 
SIM-Q
 

Tertiary/Exploratory	
Compare the effect of LY3209590 to insulin glargine for efficacy parameters	
 
Percentage of participants at Week 52 achieving:         
 
HbA1c <7%
 
HbA1c <7% without Level 2 or 3 nocturnal hypoglycemia, and
 
HbA1c ≤6.5% without Level 2 or 3 hypoglycemia
 
 
 
Change from baseline to Weeks 26 and 52 for fasting serum glucose
 

Evaluate the percentage of participants receiving LY3209590 that require a transition to the LY3209590 prefilled pen	Percentage of participants that require transition to the LY3209590 prefilled pen at Weeks 26 and 52
Evaluate the percentage of participants at each fixed LY3209590 dose level	Percentage of participants at each fixed dose level at Weeks 26 and 52

Objectives	Endpoints
Compare the effect of LY3209590 to insulin glargine for safety parameters	
 
Incidence and rate of Level 2 hypoglycemia events during treatment period
 
Incidence and rate of Level 3 hypoglycemia events during treatment period
 
Incidence of positive LY3209590 treatment-emergent antidrug antibodies
 

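### The model for insulin dose in units has no continuous baseline covariate, so its confidence intervals may be wider than necessary, although baseline weight is already collected

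*SAP*

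**What the plan says.** SAP 1.1 lists "Insulin dose at Weeks 16, 26, and 52" among the other secondary endpoints. SAP 4.4.2.1 introduces the model with "The analysis of study insulin dose will use an MMRM model on the EAS2 data with treatment, strata" and gives its terms in full: "treatment, strata (country, GLP-1 RA treatment at randomization, and baseline HbA1c stratum [<8.0%, ≥8.0%]), visit, and treatment-by-visit interaction as fixed effects". The covariance is fixed in the same section: "The variance-covariance structure in the MMRM models for fasting glucose from SMBG and insulin dose will be based on compound symmetry". The SAP 4.1 table marks the baseline for dose as not applicable, as one expects in insulin-naive participants, and takes all scheduled visits from 3 to 33 into the model.

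Weight enters only as a divisor. SAP 4.4.2.1 states "The analysis will be repeated for average daily dose in U and daily dose in U/kg" and then "The body weight at the visit will be used to calculate the daily dose in U/kg at the same visit".

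Baseline weight exists. Protocol 8.2.1 says "Height and weight will be measured as outlined in the SoA", and the Schedule of Activities marks weight at Visits 1, 2 and 3. The SAP 4.1 table defines baseline weight as the last available value up to the first dose date.

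**The concern.** HbA1c, SMBG fasting glucose and TRIM-D are each adjusted for their own baseline value. Dose has no baseline value, and nothing continuous takes its place: the only prognostic terms are country and two binary strata. A baseline measure that predicts the dose a participant reaches would remove residual variance from the arm comparison.

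Body weight is the obvious candidate. The plan itself reports dose per kilogram, and Protocol 5.1 caps BMI at 45 kg/m² with no lower limit, so weight should vary widely. It is not a stratification factor (Protocol 6.3). Baseline fasting SMBG is a second candidate, because titration in both arms is driven by fasting glucose (Protocol 6.5).

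The U/kg repeat does not do this job. It estimates a different quantity, cannot narrow the interval for dose in U, and divides by a weight measured after randomisation, which treatment may itself change. What is at stake is the precision of one supportive secondary comparison.

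**Working it through.** **Inputs.** From the documents: the model terms and compound symmetry (SAP 4.4.2.1), Visits 3 to 33 (SAP 4.1), and about 284 completers per arm (SAP 5). Assumed, because the documents give neither a dose SD nor a dose-weight correlation: r, the within-arm correlation of baseline weight with dose in U after the strata, taken from 0 to 0.5.

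**The plan's own figures.** 670 × 0.85 / 2 = 284.75 per arm, against a stated 284. With an SD of 1.1%, 284 per arm gives 99.1% power at the 0.4% margin, 90.1% at 0.3%, and 90.1% for superiority at −0.3%, in line with SAP 5. These concern HbA1c; no power or precision is stated for dose.

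**Main calculation.** The ratio of interval widths with and without the covariate is √(1 − r²). The half-width without it, in dose SDs, is 1.96 × √(2/284) = 0.1645. The equivalent gain in participants is 1/(1 − r²) − 1.

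| r (assumed) | Width ratio | Narrower by | Half-width (SD) | Equivalent extra participants |
|---|---|---|---|---|
| 0 | 1.000 | 0% | 0.1645 | 0% |
| 0.2 | 0.980 | 2.0% | 0.161 | 4% |
| 0.3 | 0.954 | 4.6% | 0.157 | 10% |
| 0.4 | 0.917 | 8.3% | 0.151 | 19% |
| 0.5 | 0.866 | 13.4% | 0.142 | 33% |

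A simulation under compound symmetry (284 per arm, five visits, within-participant correlation 0.7, the last two assumed) gave ratios of 0.981, 0.955, 0.916 and 0.864 for r = 0.2 to 0.5. It held r constant over visits, so it checks the formula and not the two complications below.

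**Different correlation in each arm.** With a common slope b = (r₁ + r₂)/2 and equal SDs, the variance ratio is the mean over arms of 1 − 2b·rᵢ + b².
- r = 0.1 and 0.4: b = 0.25, arm terms 1.0125 and 0.8625, mean 0.9375, root 0.968, so 3.2% narrower.
- r = 0.2 and 0.5: b = 0.35, arm terms 0.9825 and 0.7725, mean 0.8775, root 0.937, so 6.3% narrower.

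**A slope that grows over visits.** Everyone in an arm starts on the same dose (Protocol 6.5.1.1 and 6.5.2.1), so weight cannot predict dose at first. Compound symmetry uses one variance for all visits. With complete data, the reported Week 52 width therefore changes by √(1 − average of r² over visits), the average being weighted by each visit's dose variance. As an illustration with equal variances, take r = 0 at half the visits and 0.4 at the rest: the average r² is 0.16/2 = 0.08 and √0.92 = 0.959, so 4.1% narrower instead of 8.3%. If dose variance rises over time, later visits weigh more and the figure moves back towards 8.3%.

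**Chance imbalance in weight.** One standard error of the difference in mean baseline weight is √(2/284) = 0.084 weight SD. At r = 0.4 this shifts the dose difference by 0.4 × 0.084 = 0.034 dose SD, about a fifth of the 0.1645 half-width.

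**The case against.** The strongest reply is that the key input is missing. Protocol 6.5 individualises dose on fasting glucose and hypoglycaemia, and starting doses are flat. Nothing in the documents quantifies how far weight predicts dose; at a correlation of 0.2 or less the gain is at most 2%. A reader might infer that the intervals definitely are too wide, or that planning a U/kg analysis shows the sponsor expects a strong correlation. Neither follows: reporting dose per kilogram is ordinary practice and implies no particular correlation.

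The design may also weaken the link in one arm. Autoinjector doses take four levels with at least four weeks per step, and a reduction for hypoglycaemia is normally kept for the rest of the study, whereas glargine is reviewed weekly in small steps. This stands, and the unequal-correlation results allow for it. So does the point that a variance pooled over visits dilutes a Week 52 correlation.

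A reader might also infer that a chance imbalance in weight carries over in full to the dose difference, or biases it. It does not: only r times the imbalance carries over, randomisation keeps the estimate unbiased, and the interval already allows for that variation.

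Finally, baseline SMBG can be missing, as SAP 4.4.2.1 itself anticipates, so adding it without a rule could drop participants. That too stands and shapes the fix. None of these points is a reason to leave baseline weight out.

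**Conclusion.** The point holds as a possible loss of precision. The dose model in U has no continuous baseline covariate, a suitable one is already collected and defined, and the intervals may be wider than necessary. The size is conditional: about 0% to 13% narrower for an assumed correlation of 0 to 0.5, with a smaller gain likely at Week 52 if the slope grows over visits or the correlation is weaker in the fixed-dose arm.

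The documents do not support reading this as an error or a source of bias. Insulin dose is a supportive endpoint outside the gatekeeping in SAP 2.1, with no margin or power claim, and the primary and gated HbA1c inference is untouched. It is a low-priority improvement.

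**What to change.** In SAP 4.4.2.1, add baseline body weight (continuous, as defined in SAP 4.1) and its interaction with visit to the models for average weekly dose and average daily dose in U. The interaction is needed because the slope starts near zero under a common starting dose. Leave the U/kg analysis as planned.

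Baseline fasting SMBG may be added in the same way, provided participants without a baseline value are kept by a simple stated imputation, such as the overall mean of observed baseline values taken without regard to arm.

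The cost is a sentence or two of SAP text before unblinding, with no new data and no effect on type I error control. Visits 3 to 33 are 31 scheduled visits, so each by-visit covariate adds about 30 coefficients, which is modest against some 284 completers per arm followed over those visits. If the SAP can no longer be changed, run the adjusted model as a labelled sensitivity analysis.
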